15.4 Vital Signs

Vital signs will be collected on the 'Screening Vital Signs' and 'Vital Signs' eCRF pages.

The following vital sign parameters will be collected for this study as per the schedule of events:

- Systolic blood pressure (SBP) (mmHg)
- Diastolic blood pressure (DBP) (mmHg)

- Pulse rate (beats per minute [bpm])
- Respiratory rate (breaths/min)
- Body temperature (°C)
- Weight (kg) at baseline
- Height (cm) at baseline

The following summaries will be provided by treatment group based on the SAF analysis set for each vital sign parameter:

- Descriptive statistics and changes from baseline over time by treatment group;

All vital sign data will be listed.

15.5 Other Safety or Tolerability Evaluations

ECG data will be collected on the 'ECG' eCRF page.

ECG summaries will include all ECG assessments from the on-treatment period.

The analysis of QT data is complicated by the fact that the QT interval is highly correlated with heart rate. Because of this correlation, formulas are routinely used to obtain a corrected value, denoted QTc, which is independent of heart rate. This QTc interval is intended to represent the QT interval at a standardized heart rate. Several correction formulas have been proposed in the literature. For this analysis we will use some of those methods of correction, as described below. The QT interval corrected for heart rate by the Fridericia's formula, QTcF, is defined as

$$QTcF = \frac{QT}{\sqrt[3]{RR}},$$

where RR represents the RR interval of the ECG, in seconds, and can be estimated as 60/Heart Rate.

QTcF values collected in the eCRF will be used for the analysis. In case those are missing, this parameter will be derived based on RR and QT.

The following analyses will be performed for each of the applicable ECG parameters (ventricular rate, denoted as HR in what follows, PR, RR, QRS, QT, QTc and QTcF) by treatment group, during the on-treatment period. Unscheduled ECG measurements will not be used in computing the descriptive statistics for change from baseline at each post-baseline time point. However, they will be used in the analysis of notable ECG changes.

- For each of the ECG parameters (HR, PR, RR, QRS, QT, QTc and QTcF), descriptive statistics of absolute and changes from baseline values at scheduled time points will be reported.
- Shift to worst post-baseline investigator interpretation.
- Shift to worst post-baseline value according to the notable ECG categories presented below. Maximum post-baseline value will be used.
 - QTcF increase from baseline >30 ms, >60 ms
 - QTcF > 450 ms, > 480 ms, > 500 ms

Complete ECG profiles will be listed, and notable ECG interval value or change will be flagged.

16 Analyses of Other Endpoints

16.1 Pharmacokinetics

Population: PK Analysis Set

Non-compartmental computation of M5049 PK parameters will be performed using the computer program PPD [REDACTED] or higher PPD [REDACTED]. The statistical software SAS[®] PPD [REDACTED], Version 9.2, or higher, will be used to produce tables, listings, and figures. Figures will be prepared with SAS Version 9.2, or higher.

M5049 tables, listings, and figures will be generated using SAS.

Pharmacokinetic parameters will be calculated using standard non-compartmental methods, the actual administered dose, and actual elapsed time from dosing.

Further exploratory analyses of M5049 PK and exposure-response relationships with respect to biomarkers/clinical endpoints will be described using modeling and simulation. Full details of the relevant (integrated) population modeling and simulation activities (including objectives, relevant endpoints, methodology, software, etc.) will be defined in a separate Pharmacometry analysis plan and presented separately from the main clinical study report.

Blood will be collected for M5049 determination according to the following schedules:

Table 3: Pharmacokinetic Sampling Times for Part A

| Day | Time (h) | Time from Scheduled Sampling Allowed |
|-------|----------|--|
| Day 1 | Predose | Within 60 minutes prior to dose administration |
| | 1 | ± 20 minutes |
| | 2 | ± 20 minutes |

| Day | Time (h) | Time from Scheduled Sampling Allowed |
|-------|----------|--|
| | 6 | ± 30 minutes |
| | 12 | ± 120 minutes |
| Day 7 | Predose | Within 60 minutes prior to dose administration |
| | 1 | ± 20 minutes |
| | 2 | ± 20 minutes |
| | 6 | ± 30 minutes |

Note: Samples collected by site when possible.

Table 4: Pharmacokinetic Sampling Times for Part B

| Day | Time (h) | Time from Scheduled Sampling Allowed |
|-------------|---------------|--|
| Day 1 | Predose | Within 60 minutes prior to dose administration |
| | 1 to 2 hours | N/A |
| | 4 to 6 hours | N/A |
| | 8 to 12 hours | N/A |
| Day 3 and 7 | Predose | Within 60 minutes prior to dose administration |
| | 1 to 2 hours | N/A |
| | 4 to 6 hours | N/A |

Part A samples that are collected outside the specified time windows will be included in the PK parameter estimation (NCA) but will be excluded from the concentration summary and mean concentration plots. Part B samples that are collected outside the specified time windows will be included in the PK parameter estimation, flagged in the concentration listing, and excluded from the concentration summary and mean concentration plots.

Pharmacokinetic concentrations which are erroneous due to a protocol violation (as defined in the CSP), sampling processing or analytical error (as documented in the bioanalytical report) may be excluded from the PK analysis if agreed by the Sponsor. In this case the rationale for exclusion must be provided in the CSR. Any other PK concentrations that appear implausible to the Clinical Pharmacologist/Clinical PK/PD Scientist will not be excluded from the analysis. Any implausible data will be documented in the CSR.

Any PK concentrations or PK parameters excluded from summary statistics will be included in subject listings and flagged; a reason for exclusion will be detailed in the CSR (e.g. a footnote or a table of exclusions). Any flags should be included in the study specific SDTM and ADaM data sets.

IDMC 1 PK analysis will be based on Part A concentrations (Day 1 and Day 7-predose only) and parameters (Day 1 only), as listed below. The PK outputs for IDMC 1 are presented in Section 6.1.

The following PK parameters will be reported for M5049 on Day 1 and Day 7 in Part A only except where noted, where data permit.

| | |
|-------------------------|--|
| $AUC_{0-t_{last}}$ | Area under the concentration-time curve (AUC) from time of dosing to the time of the last quantifiable observation. |
| $AUC_{0-t_{last}}/Dose$ | The dose-normalized $AUC_{0-t_{last}}$. Normalized using the actual dose, using the formula $AUC_{0-t_{last}}/Dose$. |
| AUC_{0-12h} | AUC from time of dosing to time 12 hours post dose. AUC_{0-12h} (Day 1) will be based on the estimated concentration at 12 hours after dosing. AUC_{0-12h} (Day 7) will be based on predose Day 7 concentration used for estimated concentration at 12 hours. |
| $AUC_{0-12h}/Dose$ | The dose-normalized AUC_{0-12h} . Normalized using the actual dose, using the formula $AUC_{0-12h}/Dose$. |
| $AUC_{0-\infty}$ | AUC from time of dosing extrapolated to infinity on Day 1 only, based on the predicted value for the concentration at t_{last} , as estimated using the linear regression from λ_z determination. $AUC_{0-\infty} = AUC_{0-t_{last}} + C_{last\ pred}/\lambda_z$. |
| $AUC_{0-\infty}/Dose$ | The dose-normalized $AUC_{0-\infty}$. Normalized using the actual dose, using the formula $AUC_{0-\infty}/Dose$ on Day 1 only. |
| CL/F | The apparent total body clearance of study intervention following extravascular administration on Day 1 only, $CL/F = Dose/AUC_{0-\infty}$. |
| C_{max} | Maximum observed concentration. |
| $C_{max}/Dose$ | The dose-normalized maximum observed concentration. Normalized using the actual dose, and the formula $C_{max}/Dose$. |
| C_{trough} | The concentration observed immediately before next dosing on Day 7 only. |
| λ_z | Terminal first order elimination rate constant. |
| $R_{acc}(AUC_{0-12h})$ | The accumulation ratio of AUC_{0-12h} from Day 1 to Day 7. $R_{acc}(AUC_{0-12h}) = AUC_{0-12h}(Day\ 7)/AUC_{0-12h}(Day\ 1)$ |
| $R_{acc}(C_{max})$ | The accumulation ratio of C_{max} from Day 1 to Day 7. $R_{acc}(C_{max}) = C_{max}(Day\ 7)/C_{max}(Day\ 1)$ |
| t_{max} | Time to reach the maximum observed concentration C_{max} . |
| $t_{1/2}$ | Apparent terminal half-life, $t_{1/2} = \ln 2/\lambda_z$. |
| V_z/F | The apparent volume of distribution during the terminal phase following extravascular administration on Day 1 only, $V_z/F = Dose/(AUC_{0-\infty} \times \lambda_z)$. |

The following PK parameters will be calculated for M5049 for diagnostic purposes and listed, but will not be summarized:

- First ($\lambda_{z\ low}$) and last ($\lambda_{z\ up}$) time point of the time of the log-linear regression to determine λ_z .
- Number of data points included in the log-linear regression analysis to determine λ_z .
- Goodness of fit statistic (Rs_{q,adj}) for calculation of λ_z .
- AUC_{extra}: The AUC from time t_{last} extrapolated to infinity given as percentage of AUC_{0-∞}. $AUC_{extra} = (\text{extrapolated area}/AUC_{0-\infty}) * 100$.

The following PK parameters will be reported for M5049 on Day 1, Day 3, and Day 7 in Part B only except where noted, where data permit.

| | |
|---------------------|--|
| C _{max} | Maximum observed concentration. |
| C _{trough} | The concentration observed immediately before next dosing on Day 3 and 7 only. |
| t _{max} | Time to reach the maximum observed concentration C _{max} . |

The calculation of the AUC will be performed using the mixed linear-log trapezoidal method. The actual time of blood sampling (14 significant digits or the SAS format Best12) will be used for PK parameter calculation. In cases where the actual sampling time is missing, calculations will be performed using the scheduled time.

Values below the lower limit of quantification of the assay (LLOQ) will be taken as zero for summary statistics of PK concentration data, PK parameter estimation, and for graphical presentations. In case BLQ concentrations occur at the end of the dosing interval (12 h), these concentrations will be excluded from the calculation of the AUC₀₋₁₂.

The regression analysis should contain data from at least 3 different time points in the terminal phase consistent with the assessment of a straight line on the log-transformed scale. PPD “best fit” methodology will be used as standard. However, in some cases, further adjustment may be made by the pharmacokineticist, if warranted, after agreement with the Sponsor. The last quantifiable concentration should always be included in the regression analysis, while the concentration at t_{max} and any concentrations <LLOQ which occur after the last quantifiable data point should not be used.

The coefficient of correlation (Rs_{q,adj}) should be ≥ 0.8000 , AUC_{extra} should not be greater than 20%, and the observation period over which the regression line is estimated should be at least twofold the resulting t_{1/2} itself. If these criteria are not met, then the rate constant and all derived parameters (CL/F, V_z/F, t_{1/2}, AUC_{0-∞}, and AUC_{0-∞}/D) will be included in the parameter listings and descriptive statistics but will be flagged in listings and discussed appropriately.

The following listings and summary statistics of M5049 PK concentration and parameter data will be provided, where data permit:

- Listing of individual PK concentration data by part, dose, day, and scheduled time point

- Listing of individual single dose PK parameters by part and dose
- Listing of individual multiple dose PK parameters by part and dose
- Descriptive summary table of PK concentration data by dose, day, and scheduled time point (Part A) or time window (Part B)
- Descriptive summary table of PK parameter data by part, dose, and day
- Individual concentration-time profiles (linear and semi-logarithmic scales) will be plotted by part, dose level, and day as spaghetti plots, using actual time points (where available).
- Arithmetic mean concentrations will be plotted on both linear (\pm SD) and semi-logarithmic scales using scheduled time points – with all dose levels overlaid by part and day. Part B will use the midpoint of the allowed sampling window for the time value when plotting.
- Scatter plots of dose-normalized C_{max} , dose-normalized AUC_{0-12h} , dose-normalized AUC_{0-last} , and dose-normalized $AUC_{0-\infty}$ (as applicable) against dose for each corresponding day, where applicable. (Part A only)
- Scatter plot of C_{max} against dose for each corresponding day, where applicable. (Part B only)

All descriptive summaries of PK data will be performed using the PKAS. Individual PK data will be listed using the ITT Analysis Set. The mean concentration-time profiles and PK parameter plots will be plotted using the PKAS and the individual subject concentration-time profiles will use the ITT Analysis Set.

Exploratory dose proportionality analysis for Part A will be performed by visual inspection of the scatter plots of $C_{max}/dose$, $AUC_{0-12h}/dose$, $AUC_{0-last}/dose$, and $AUC_{0-\infty}/dose$ versus dose (where available).

PPD NCA Core Output will be provided in a separate listing.

17 **References**

Yeonhee Kim and Seunghyun Won. “Adjusted proportion difference and confidence interval in stratified randomized trials.” PharmaSUG 2013 - Paper SP04

18 Appendices

18.1 Appendix 1 - NCI-CTC Gradable and Non-Gradable Safety Laboratory Test Parameters and Direction(s) of Abnormality

NCI-CTC gradable parameters

| Laboratory Assessment | Parameters | Name in NCI-CTC | Direction(s) of abnormality |
|-----------------------|----------------------------------|---|-----------------------------|
| Hematology | Hemoglobin | Anemia / Hemoglobin increased | Low/High |
| | Leukocytes (WBC) | White blood cell decreased / Leukocytosis | Low/High |
| | Neutrophils | Neutrophil count decreased | Low |
| | Eosinophils | Eosinophilia | High |
| | Lymphocytes | Lymphocyte count decreased / increased | Low/High |
| | Platelets | Platelet count decreased | Low |
| Biochemistry | Albumin | Hypoalbuminemia | Low |
| | Alanine Aminotransferase (ALT) | Alanine Aminotransferase increased | High |
| | Aspartate Aminotransferase (AST) | Aspartate Aminotransferase increased | High |
| | Alkaline Phosphatase (ALP) | Alkaline Phosphatase increased | High |
| | Bicarbonate | Blood Bicarbonate decreased | Low |
| | Total Bilirubin | Blood bilirubin increased | High |
| | Creatinine | Creatinine increased | High |
| | Creatine Kinase (CK) | CPK increased | High |
| | Sodium | Hyponatremia / Hypernatremia | Low / High |
| | Potassium | Hypokalemia / Hyperkalemia | Low / High |
| | Glucose | Hypoglycemia | Low |

Note: parameters with both Low and High directions of abnormality are going to be split. For example, Calcium is going to be split in Calcium Low and Calcium High.

NCI-CTC non-gradable parameters

| Laboratory Assessment | Parameters | Direction of interest |
|-----------------------|------------|-----------------------|
| Hematology | Hematocrit | |

| Laboratory Assessment | Parameters | Direction of interest |
|------------------------------|---|------------------------------|
| | Mean corpuscular volume (MCV) | High |
| | Basophils | |
| | Monocytes | High |
| Biochemistry | Total Protein | Low |
| | Chloride | High |
| | Urea Nitrogen (BUN) | High |
| | Estimated Glomerular Filtration Rate (eGFR) | Low |

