Serum virology (hepatitis B and C screening, HIV)	X														Data collected from chart: virology status is to be documented per local guidelines. A positive test result is NOT exclusionary but for participant management. Evaluations to be performed by local laboratory.	
Urine for drugs of abuse	X													X	Data collected from chart: status to be documented per local guidelines. A positive test result for nonprescribed drugs is NOT exclusionary but for participant management. Evaluations to be performed by local laboratory.	

Assessments and Procedures	SCR	Intervention Period (Days)							Continued Surveillance		Safety Follow-up		Relapse Admission ^a	Notes	
							HD/ET	EoT				EoS			
	(up to 48 hours before Day 1)													HD assessments should occur if participant discharged after Day 3 and before Day 14. ET (early termination of treatment) Visit should occur within + 24 hours of treatment discontinuation.	
Study Day		1	2	3	5	7	10		14	21	28	44	60	5 to 60	
Visit Window			± 6 h		± 12 h		± 24 h			+ 2 days		± 5 days	± 7 days	± 6 h	
Clinical Assessments and Study Intervention															
Study intervention administration		←Throughout 14 days→						X						X	Every 12 hours ± 2 hours for 14 days (4 tablets in the morning and 4 tablets in the evening).
Study intervention accountability		←-----Throughout (daily)-----→												X	Date and time of study intervention administration should be recorded daily, if discharged before EoT, date and time to be recorded on diary card.
Clinical surveillance scoring (9-point ordinal scale)		←-----Once daily during hospitalization (incl. predose on Day 1) and at the time of hospital discharge. After hospital discharge, then at study visits (e.g., Days 3, 5, 7, 10, 14, 21, 28, 44, and 60) and clinical status change-----→												Record each day throughout hospitalization at the first assessment of a given study day and at the time of hospital discharge; after participant is discharged, either via telemedicine contact or by return to study site at the times indicated only. The scale includes information such as hospitalization discharge, ICU stay, mechanical ventilation.	
Adverse event review		←-----Throughout-----→												Record each day at approximately the same time throughout hospitalization; if participant is discharged, either via telemedicine contact or by return to study site at the times indicated only.	

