Postdose PK		X	X			X									
See PK instructions for sampling window.
 
Part A Day 1: 1, 2, 6, and 12 hours postdose (12 hours postdose sampling must be done prior to the second dose on Day 1).
 
Part A Day 7: 1, 2, and 6 hours postdose.
 
Part B Day 1: 1-2 hours postdose, 4-6 hours postdose and 8-12 hours postdose (8-12 hours postdose sampling must be done prior to the second dose on Day 1).
 
Part B Day 3 and Day 7: 1-2 hours postdose and 4-6 hours postdose.
 
For 1-hour postdose PK, identify and record the time of the closest meal consumed after the study intervention administration, i.e., when the first meal started after study intervention administration (unless participant is discharged).
 
PK evaluations to be performed by central laboratory.
 
Note: Selected sites for Part A and Part B will not perform sampling at 4 to 6 hours and 8 to 12 hours postdose on Day 1, Day 3, or Day 7.

Assessments and Procedures	SCR	Intervention Period (Days)							Continued Surveillance		Safety Follow-up			Relapse Admission ^a	Notes
									HD/ET	EoT			EoS		
Study Day		1	2	3	5	7	10		14	21	28	44	60	5 to 60	
Visit Window		± 6 h		± 12 h		± 24 h			+ 2 days		± 5 days	± 7 days	± 6 h		
Serum biomarkers		X		X		X		X	X					X	Evaluations to be performed by central laboratory. Day 1 sample must be collected prior to study intervention administration. Record time each sample collected. E.g., other cytokines, anti-SARS-CoV-2 antibodies; collect unless participant is discharged and not seen at study site. Day 3 sample collected in Part B only.

[figure not shown]

ALT = alanine aminotransferase, AST = aspartate aminotransferase, BUN = blood urea nitrogen, CK = creatinine kinase, COVID-19 = coronavirus disease 2019, Cr = creatinine, CRP = C-reactive protein, CT = computed tomography, ECG = electrocardiogram, eGFR = estimated glomerular filtration rate; EoS = End of Study, EoT = End of Treatment, ET = Early Termination of treatment, FiO₂ = fraction of inspired oxygen, HCT = hematocrit, HD = hospital discharge, Hgb = hemoglobin, HIV = human immunodeficiency virus, ICU = intensive care unit; IFN = interferon, IWRS = Interactive Web Response System, NAT = nucleic acid test, PK = pharmacokinetic, RNA = ribonucleic acid, SARS-CoV-2 = severe acute respiratory syndrome coronavirus, SCR = Screening, SoC = standard of care, SpO₂ = peripheral capillary oxygen saturation, TB = tuberculosis, TP = total protein, WBC = white blood cell.

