2.1 Study Rationale

Coronavirus disease 2019 (COVID-19) is a new pandemic disease characterized by pulmonary inflammation from infection with severe acute respiratory syndrome coronavirus 2 (SARS-CoV-2). SARS-CoV-2 is a single-stranded ribonucleic acid (ssRNA) virus related to both SARS-CoV-1, which caused severe acute respiratory syndrome (SARS) disease in 2002/03, and Middle East respiratory syndrome coronavirus. While antiviral therapies to treat the COVID-19 are urgently needed, treatments for severe disease with excessive pulmonary inflammation are also critical to reduce COVID-19 complications leading to increased mortality and to decrease the burden of the rapidly evolving pandemic on the health care system (Feldmann 2020). Given that the immunopathology in reaction to SARS-CoV-2 infection is contributing to the high rate of morbidity and mortality, host-directed immunomodulatory approaches are also being evaluated (Mehta 2020, Stebbing 2020).

In this exploratory Phase II study, a 14-day course of M5049, a potent, selective toll-like receptor (TLR) 7/8 antagonist will be evaluated. The optimal timing of M5049 dosing is hypothesized to be after the participant's initial antiviral response (so as to not interfere with initial host control or clearance of the virus) and when increasing pulmonary inflammation is signaling an overly amplified host inflammatory response. Treatment of COVID-19 pneumonia after the immediate host innate and early adaptive immune responses could potentially halt progression to severe immunopathology without compromising viral clearance (Siddiqui 2020).

The safety and clinical response to orally-administered M5049 will be evaluated for 14 days in participants with moderate to severe COVID-19 pneumonia who are maintained on local standard of care and hospitalized without the need for mechanical ventilation. The 2-part study is a randomized, double-blind, placebo-controlled design. The study design and participant safety monitoring are based on M5049 data obtained from the first-in-human (FIH) Phase I single ascending dose and 14-day multiple ascending dose healthy volunteer study, nonclinical evaluations of M5049, and the timing of other anti-inflammatory agents for treatment of COVID-19 pneumonia. M5049 demonstrates dose-proportional pharmacokinetics (PK), has a half-life of approximately 7 to 11 hours, and is mainly metabolized by aldehyde oxidase, not the common cytochrome P450 enzymes.

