4.3 Justification for Dose

The proposed doses of M5049 for the study are 50 mg or 100 mg twice daily in a new tablet formulation without food restriction. The dose levels to be evaluated are selected based on safety, PK, and PD (inhibition of ex vivo-stimulated IL-6 cytokine secretion) observed in the single and multiple ascending dose (FIH) study in healthy participants. Pharmacokinetic results indicated dose-proportionality of maximal concentrations and overall exposure (AUC) in the investigated dose range (1 to 200 mg single or as daily dose) with a terminal half-life of 7 to 11 hours.

The following data were considered when determining the doses of M5049 for this study:

- Preliminary modeling and simulations based on the observed PK and PD (inhibition of ex vivo-stimulated IL-6 cytokine secretion) in the FIH study suggest that M5049 trough concentrations at steady-state ($C_{min,ss}$) will remain above the IC_{90} in 87.3% of the participants who receive a 100 mg twice daily dose and 31.2% of participants who receive a 50 mg twice daily dose. For both the 50 mg and 100 mg twice daily doses, M5049 trough concentrations will remain above the IC_{50} in more than 90% of participants.
- The FIH healthy volunteer study evaluated an oral M5049 solution under fasted condition except for a small food effect cohort. The current study will use a tablet formulation without food restriction. M5049 is considered as a Biopharmaceutics Classification System Class 1 compound and tablet formulation showed very rapid dissolution profile. It is expected that the new tablet formulation has similar exposure compared to the oral solution used in the FIH study.

- The expected $AUC_{0-24h,ss}$ and $C_{max,ss}$ at 100 mg twice daily without food restriction remains well below the exposures at the no observed adverse effect levels in 4-week nonclinical toxicology study in dog with at least 10-fold safety margin.
- The AUC was increased by 33% and C_{max} was decreased by 11% under fed condition compared to fasted conditions.

Based on the above considerations, both the 50 mg and 100 mg twice daily doses in the new tablet formulation without food restrictions may provide the opportunity to observe a PD effect (i.e., suppression of inflammatory biomarkers, e.g., IL-6) and clinical response in participants with COVID-19 pneumonia while also maintaining acceptable safety margin.

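### At the stated half-life of 7–11 h, Part A Day 1 sampling is too short for the SAP's own terminal-phase criteria, yet failing values enter the PK summary tables unmarked

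*SAP*

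**What the plan says.** **Half-life.** Protocol 2.1 says M5049 "has a half-life of approximately 7 to 11 hours". Protocol 4.3 repeats a "terminal half-life of 7 to 11 hours" from the healthy-volunteer study.

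**Sampling.** The postdose PK row of the schedule (Protocol 1.2) gives "Part A Day 1: 1, 2, 6, and 12 hours postdose", with the condition that "12 hours postdose sampling must be done prior to the second dose on Day 1". It then gives "Part A Day 7: 1, 2, and 6 hours postdose", in addition to a predose sample. SAP 16.1, Table 3, has the same times. Dosing is "Every 12 hours ± 2 hours for 14 days".

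**Criteria (SAP 16.1).** The regression needs at least three terminal-phase time points, must include the last quantifiable concentration and must leave out the concentration at tmax. Adjusted R-squared should be at least 0.80, and extrapolated AUC should not exceed 20%. In addition, "the observation period over which the regression line is estimated should be at least twofold the resulting" half-life.

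**When criteria fail.** The rate constant, CL/F, Vz/F, t1/2, AUC0-∞ and its dose-normalised form "will be included in the parameter listings and descriptive statistics but will be flagged in listings and discussed appropriately". The per-profile diagnostics (regression limits, number of points, adjusted R-squared, extrapolated share) are listed but not summarised.

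**Which days.** SAP 16.1 limits AUC0-∞, CL/F and Vz/F to Day 1. It sets no such limit for lambda-z and t1/2, so these are planned for Day 7 too, where the data allow.

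**The concern.** Criteria of this kind are meant to pick out the occasional poor profile. Here the sampling schedule and the expected half-life conflict, so failure would be the rule. The Part A summary tables would then show geometric means and confidence intervals (SAP 9.2.2), from about five participants per active dose, for parameters that mostly miss the plan's own criteria. Nothing in those tables would say so, because the flag is specified for listings only. AUC0-∞/dose also feeds the visual check of dose proportionality. At stake is how far a reader can rely on the reported half-life, clearance and volume, which are named Part A secondary endpoints.

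**Working it through.** The documents give no figure of their own to reproduce here. The check compares the schedule with the criteria.

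**Inputs.** Half-life 7–11 h (Protocol 2.1, 4.3). Day 1 samples at 1, 2, 6 and 12 h, and Day 7 samples predose and at 1, 2 and 6 h (Protocol 1.2; SAP Table 3). Windows of ±20 min at 1 and 2 h and ±120 min at 12 h (Protocol Table 4). Span at least 2 × t1/2, extrapolated AUC at most 20%, at least three points without tmax (SAP 16.1).

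**1. Span, Day 1.** The 1 h sample is the first after dosing, so it is either the observed tmax, which is excluded, or lies before the peak. The earliest usable point is therefore 2 h, and only if tmax falls at 1 h.
- Longest nominal span: 12 − 2 = 10 h. Required: 2 × 7 = 14 h to 2 × 11 = 22 h.
- Half-lives covered: 10/7 = 1.43 to 10/11 = 0.91, against 2.
- Longest half-life that passes: 10/2 = 5.0 h.
- Both windows stretched (1.67 h to 14 h): span 12.33 h, so the longest passing half-life is 12.33/2 = 6.2 h, still below 7 h.

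This step needs no compartment model.

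**2. Extrapolated AUC, Day 1.** Assume one compartment with immediate input, so the share beyond time T is exp(−ln2 × T/t1/2).

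| t1/2 | T = 12 h | T = 14 h |
|---|---|---|
| 7 h | 30.5% | 25.0% |
| 9 h | 39.7% | 34.0% |
| 11 h | 46.9% | 41.4% |

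With oral absorption (assumed ka of 1 to 5 per h), the 12 h figures become 31–34% at 7 h and 48–50% at 11 h. Reaching 20% at 12 h needs t1/2 ≤ 12 × ln2/ln5 = 5.2 h.

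**3. Number of points.** On Day 1, tmax at 2 h leaves only 6 and 12 h, one short of three. On Day 7 at most 2 and 6 h follow tmax. Using the predose value as a 12 h point, as the SAP does for AUC0-12h, would give three points but again a 10 h span.

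**4. How many would pass by chance.** The rule tests the estimated half-life, so error and between-participant variation let some profiles through. The simulation assumes one compartment, ka 3 per h, residual CV 10–30% and half-life CV 20–30%, at nominal times.

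| Mean t1/2 | Slope estimable | Meets R-squared, span and AUC limits | Passing, as share of estimable |
|---|---|---|---|
| 7 h | 50–63% | 3–8% | 5–14% |
| 9 h | 44–57% | 0–3% | 0–6% |
| 11 h | 40–53% | 0–1% | 0–2% |

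Part A has 15 × 2/3 = 10 participants on active drug, so fewer than one is expected to pass (at most 10 × 0.08 = 0.8).

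**The case against.** The plan foresees failures. It flags them in listings, discusses them, lists the diagnostics for each profile and reports only where data permit. The criteria are worded as recommendations, and the SAP never calls failing values unreliable. A reader might infer that the plan presents values it has itself disowned, but the text does not support that. What stands is narrower: neither the flag nor the diagnostics reach the summary table.

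A reader might also infer that the criteria can never be met. That goes too far. The 7–11 h range is approximate and comes from healthy volunteers, mostly fasted and given an oral solution. The rule is applied to each participant's estimate, and an estimate of about 5 h or less would pass at nominal times. Passing is not proof of reliability either. If disposition has two phases, which the documents do not say, a 2–12 h fit can return a half-life below 5 h when the terminal value is 7 h or more.

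The Day 7 problem should not be read as more misleading means. With fewer than three usable points, the likely result is an empty cell.

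It is tempting to summarise only the profiles that pass. That would select short estimated half-lives and bias the summaries, and with two or fewer profiles SAP 9.2.2 shows only n, minimum and maximum. Keeping all values with a clear mark is the better of those two choices.

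Finally, this is descriptive Part A PK in about 10 participants. Cmax and AUC0-tlast are unaffected, and AUC0-12h largely so. That limits the weight of the point. Pooling Parts A and B does not remove it, because PK parameters are tabulated by part.

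**Conclusion.** The point holds at the documents' own half-life. The Day 1 regression span is at most 10 h, or 1.4 to 0.9 half-lives against 2, and it falls short across 7–11 h even with every window stretched. Extrapolated AUC is about 30–47% against a 20% limit. That second figure rests on a one-compartment assumption; the span result does not. Under the simulated variability, 86–100% of the Day 1 slopes that can be estimated would miss at least one criterion. They would still enter the summary tables unmarked, although they are flagged in listings and discussed. Day 7 lambda-z and t1/2 will generally not be estimable under the three-point rule. This is a cheap and worthwhile correction to a secondary descriptive objective, with no bearing on efficacy or on the main exposure measures.

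**What to change.** 1. Add steady-state clearance, CL/F = Dose/AUC0-12h on Day 7, as the summarised Part A clearance, with AUC0-12h and Cmax as the main exposure measures. The SAP already derives Day 7 AUC0-12h with predose as the 12 h value. Day 7 starts about 144 h after the first dose, which is 144/11 = 13 half-lives even at 11 h, so steady state is a fair assumption if dosing was regular. State that assumption. Report the number of participants contributing, since Protocol 4.1 collects research samples only from those still in hospital.
2. Do not average only the passing profiles. Either list lambda-z, t1/2, AUC0-∞, CL/F and Vz/F for Day 1 without summary statistics, or show beside each statistic the number of profiles failing each criterion and the range of extrapolated AUC. SAP 16.1 already allows for parameters that are listed and flagged but left out of summaries.
3. Remove lambda-z and t1/2 on Day 7. Take half-life and volume from the population PK analysis already planned (Protocol 10.4.5; SAP 16.1). Record the departure from the protocol's endpoint list in SAP Section 7.

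The cost is SAP wording and fewer tabulated non-compartmental parameters. No new samples are needed.
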